7.1 Recruitment and Pre-screening

The research coordination team may develop materials to aide in recruitment. This may include, but is not limited to, informational videos and brochures which provide education about erectile dysfunction and include information about the study; physician referral letter templates which can be used to promote awareness of the study in the urology community; flyers/posters which can be utilized at approved clinic locations and as part of health fair materials; templates for print advertisements which can be utilized in

newsprint and media campaigns. Not all materials have been developed prior to trial initiation, however each of these recruitment methods will be reviewed and approved by the IRB prior to use.

Pre-screening of subjects includes reviewing medical records and imaging studies for inclusion/exclusions prior to consent. From the review of subjects' medical records and imaging studies on file, subjects who are determined to have a diagnosis of erectile dysfunction of organic origin, and have mild-moderate erectile function as assessed by IIEF-EF, as stated in Section 6.1, and also do not have evidence in their medical record of study exclusions stated in Section 6.2, are eligible to be consented to the study.

Investigators will inform research staff of potential participants who have been identified through pre-screening so the subjects can be approached to discuss the study and conduct the informed consent session. No study procedures will take place prior to the subjects signing of the informed consent form.

7.2 Payment to Subjects

No payments will be made to subjects as compensation for their participation in this study. The subjects will not be asked to pay for the treatments or participation in study either.

7.3 Informed Consent

7.3.1 Consenting Process

All subjects must provide written consent to participate in this study. An informed consent form (ICF) will be given to each subject. The ICF will contain all United States federally required elements, all International Conference of Harmonization of Technical Requirements for Registration of Pharmaceuticals for Human Use (ICH) required elements, and Health Insurance Portability and Accountability Act Authorization (HIPAA) information in language that is understandable to the subject. The informed consent includes descriptions of all study related procedures, all possible risks to participant, and the time commitment involved with participating. All consent forms will have IRB approval. The ICF and review must be in a form understandable to the subject. Translation of ICFs will be done in accordance with local IRB procedures.

Potential participants will be approached by one of the study investigators or research coordinators. Information regarding study participation will be provided to the potential participant prior to consent. Subjects will be given ample time to review the ICF and ask questions before signing. The Investigator or designee and the subject must both sign and date the ICF after review, and before any study procedures are performed. The subject will receive a copy of the signed and dated form, and the original will be retained in the site study files. The research staff member obtaining consent will document the informed process in the subject's chart for monitoring purposes. The Investigator or his/her designee must emphasize to the subject that study participation is entirely voluntary and that consent regarding study participation may be withdrawn at any time without penalty or loss of benefits to which the subject is otherwise entitled.

7.3.2 Non-English Speaking Subjects

In addition to English-speaking subjects, Spanish-speakers will also be included in the trial. A certified translated version of the IRB approved English consent form will be made

available to non-English speakers. Spanish version questionnaires and other patient-facing materials will also be made available.

7.4 Withdrawal Criteria

All subjects who either screen fails, is withdrawn from the study, or has completed all visits should be de-enrolled from the research database within 2 business days, in accordance with university policies (or respective institutional policy).

Subjects may be withdrawn from the study for any of the following reasons:

- a) A subject does not meet the eligibility criteria (the subject will be considered a screen failure).
- b) A subject withdraws consent
- c) A subject expires during protocol participation from causes other than the study treatment (not due to adverse events)
- d) At the discretion of the principal investigator for issues of non-compliance, or other behavioral factors.

8. Procedures Involved

72 men with Erectile Dysfunction (ED) of organic origin, that meet all of the inclusion and none of the exclusion criteria, will be randomized to receive either PRP, or placebo in a 1:1 double-blinded fashion.

- a) Group A (40 subjects): Autologous PRP injection. All subjects in this group will receive 2 sessions of autologous PRP penile injection with 30 ± 7 day treatment interval. 10mL of PRP will be injected at each session.
- b) Group B (40 subjects): Placebo (Normal Saline). All subjects in this group will receive 2 sessions of normal saline penile injection with 30 ± 7 day treatment interval. 10mL of normal saline will be injected at each session.

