5.1 Additional Study Sites

No additional study sites.

6. Study Population

80 males with ED of organic origin. All patients will be regular PDE5i users/responders. After a 1-month wash-out period for PDE5i, men with ED will be evaluated by IIEF-EF domain and eligible patients will be randomized to one of 2 treatment groups with an equal allocation ratio (1:1). Participants who do not adhere to the 1-month wash-out period, or do not meet the IIEF-EF domain score will be considered a screen failure and will not receive the study therapy.

6.1 Inclusion criteria: In order to participate in this study, a patient must:

- 1) Be Male
- 2) Be 30 to 75 years of age (inclusive).

- 3) Be able to provide written informed consent.
- 4) Have a diagnosis of ED due to organic origin for at least 6 months prior to consent.
- 5) Sexually active in a stable, heterosexual relationship of more than three months duration.
- 6) IIEF-EF score 11-25 at screening (even if taking a single PDE5).
- 7) Agree to attempt sexual intercourse at least 4 times per month for the duration of the study without being under the influence of alcohol or recreational drugs.
- 8) Agree to comply with all study related tests/procedures.

6.2 Exclusion criteria: In order to participate in this study, a patient must not:

- 1) Previous penile surgery of any kind (except circumcision and condyloma removal), such as penile lengthening, penile cancer surgery, penile plication, grafting.
- 2) Previous history of priapism or penile fracture
- 3) Abnormal morning serum testosterone level defined as a value lower than 300 ng/dL ($\pm 5\%$) (indicative of untreated hypogonadism), or greater than 1197 ng/dL ($\pm 5\%$).
- 4) Current or previous hormone usage, other than prescribed testosterone, clomiphene or thyroid medication. (Subjects with prior or current use of hormonal treatment for prostate cancer are also excluded.
- 5) Psychogenic ED as determined by study investigator.
- 6) Anatomical (Peyronie's Disease or penile curvature that negatively influences sexual activity) or neurological abnormalities in the treatment area.
- 7) Patients using ICI for management of ED
- 8) Patients with generalized polyneuropathy, or neurological conditions irrespective of cause, such as severe diabetes, multiple sclerosis or Parkinson's disease.

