8.2 Description of Study Procedures

8.2.1 *Informed Consent:* Refer to Section 7.3 for details regarding the informed consent process. Study procedures will be completed only after participants have signed the informed consent documentation.

8.2.2 *Demographics:* Demographic characteristics will be recorded including: date of birth, gender, marital status, race and ethnicity. If Medical history has been recorded as part of their participation in another study those source documents may be requested and used for the purpose of this research study.

8.2.3 *Medical History:* Assessment of current and past medical, surgical, and social history will be conducted.

8.2.4 *Physical Examination:* Genitourinary/Reproductive system physical exam will be performed.

8.2.5 *Doppler Ultrasound:* Penile Doppler ultrasound will be performed as standard of care for the management of erectile dysfunction. Results from within the past 12 months can be extracted from the medical record for use in this study.

8.2.6 *Concomitant Medications:* Review of current use of prescription and over the counter (OTC) medications. Participants must discontinue use of PDE5i medications throughout the duration of the study.

8.2.7 *Review Adverse Events:* Refer to Section 12 for description and reporting of adverse and serious adverse events

8.2.8 *Randomization:* Refer to Section 9.3 for details about randomization plan

8.2.9 *Study Therapy Injection:* Approximately 120mL of blood will be collected from participants for preparation of investigational product. Refer to Section 9.2 for description of IP preparation and administration.

8.2.10 *International Index of Erectile Function (IIEF) Questionnaire:* This validated 15-item self-evaluation scale provides pre and post treatment clinic evaluations of erectile function, orgasmic function, sexual desire, satisfaction in sexual intercourse and general satisfaction. If the subject has completed the IIEF questionnaire within the past 6 months, those results may be requested and used for the purpose of this research study. Questionnaires will be completed prior to therapy at injection visits.

8.2.11 *Sexual Encounter Profile (SEP3) Questionnaire:* This 5-item questionnaire is completed after each sexual intercourse attempt. Participants will be asked to complete the short version consisting of question #2 and #3 only.

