13.1 Data Analysis Plan

Analysis plan: Continuous data will be analyzed using ANOVA with repeated measures, or student's T-Test (where applicable) in order to compare differences between the treatment and control groups. For categorical data, Fisher's Exact test to determine differences between groups. Statistical significance will be evaluated using $\alpha=0.05$.

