13.2 Sample Size

Inclusion Criteria are men with IIEF scores >11 which includes men with mild (IIEF 16-21) and mild/moderate (12-16) Erectile dysfunction. Minimal clinically important differences (MCID) for these groups are an increase of 2 for mild and 5 for moderate ED. Previous studies on the effect of placebo show about a 15% improvement in men with mild to moderate ED. Therefore, 15% of the placebo group is expected to meet MCID. Results from the PRP safety study by Matz et al. 2018, which showed a mean improvement in IIEF of 4.14 points in seven patients with ED after PRP. In the interventional group, we expect 50% to meet MCID. At 80% power, we will therefore need 30 patients in each group to detect a difference of 35% between treatment and placebo arms.

$$\text{Sample size} = \frac{2(Z_{\alpha/2} + Z_{\beta})^2 P(1 - P)}{(p_1 - p_2)^2}$$

$$28.08 = (2*(1.96+0.84)^2 * (0.25*(1-0.25)) / (0.35^2)$$

Assuming attrition of approximately 20%, an additional 6 participant slots will be added to each group for a total sample size of 80 subjects.

14. Risks to Subjects

We anticipate there to be few adverse events related to the study. Based on the four published studies and abstracts, including 75 men, only minor adverse events were reported (Bruising 1, Mild Pain 4). No serious adverse events were observed [23-26] (Table 2). After literature review, we believe this product to be of non-significant risk to patients (NSR) and for investigational use in a clinical study protocol.

Based on published studies, we will record anticipated adverse events to patients include: local injection site reaction, penile pain and penile bruising. Additionally, we anticipate

patients may experience, penile swelling, allergic reaction, local infection (though none reported in previous studies) and will record them at every visit systematically.

15. Potential Benefits to Subjects

The potential benefits for men randomized to the treatment arm will include improvement in erectile function and sexual performance.

16. Privacy & Confidentiality

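### Withdrawal for non-compliance (7.4(d)), with no later outcome collection described and no analysis set named, can remove treatment failures selectively from the week-4 responder comparison

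*Combined protocol and SAP*

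**What the plan says.** Section 7.4(d) lists as a ground for withdrawal from the study: "At the discretion of the principal investigator for issues of non-compliance, or other behavioral factors". The same section has withdrawn men de-enrolled from the research database within 2 business days. No outcome collection after withdrawal is described there or in the visit descriptions.

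Section 8.2.6 says: "Participants must discontinue use of PDE5i medications throughout the duration of the study". Section 8.3.1 repeats the ban. Section 6 describes the population: "All patients will be regular PDE5i users/responders".

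The primary endpoint (Section 4.1) is the percentage of subjects in each group who reach the MCID in IIEF-EF at 4 weeks after the final treatment. Section 13.1 names Fisher's exact test for categorical data and a 0.05 significance level. It gives no analysis population, no missing-data rule, and no rule for men who were withdrawn or used PDE5i before the week-4 score. Section 10.1 asks only that missing data be explained.

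On sample size, Section 13.2 states that "15% of the placebo group is expected to meet MCID", expects 50% on PRP, and concludes: "At 80% power, we will therefore need 30 patients in each group to detect a difference of 35% between treatment and placebo arms". It then adds: "Assuming attrition of approximately 20%, an additional 6 participant slots will be added to each group for a total sample size of 80 subjects".

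**The concern.** The primary result is a proportion, so it depends on who is in the denominator. Each man in the trial has, by the protocol's own description, another treatment that works for him and that he may not use. The primary visit comes about 58 days after randomisation (second injection at day 28, visit about 30 days later), after a one-month wash-out. A man who sees no benefit has the most reason to go back to PDE5i. In the plain sense of the word that is non-compliance, for which the investigator may withdraw him.

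If such a man leaves before week 4 and no score is collected, a treatment failure disappears from the comparison because he failed. Responder percentages among the men who remain then rise. If failures leave at different rates in the two arms, the comparison is biased even when PRP has no effect. The plan contains nothing to prevent this and nothing that says how such men count.

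**Working it through.** **The plan's own figure.** Inputs from Section 13.2: 15% v 50%, z-values 1.96 and 0.84, difference 0.35. The formula is n = 2(1.96 + 0.84)² P(1 − P) / 0.35². With P = (0.15 + 0.50)/2 = 0.325, n = 2 × 7.84 × 0.219375 / 0.1225 = 28.08, which matches the printed result and is close to the stated 30. The printed substitution, "28.08 = (2*(1.96+0.84)^2 * (0.25*(1-0.25)) / (0.35^2", uses P = 0.25 and would give 24.0. Also, 30 + 6 = 36 per group is 72 in total, not 80. Both are separate matters. I use the stated 40 per arm below; 20% attrition leaves 32.

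**Planned rates, failures lost at an equal rate.** Of 40 per arm, the failures are 20 on PRP and 34 on placebo, 54 in all. Assume that all the planned attrition (20% of 80 = 16 men) falls on failures, at 16/54 = 29.6% in each arm.
- PRP: 20 − 5.93 = 14.07 failures remain; 20/34.07 = 58.7%.
- Placebo: 34 − 10.07 = 23.93 failures remain; 6/29.93 = 20.0%.
- Difference: 38.6 points, against a true 35.

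**Direction.** With a fraction r of failures lost, the rate among men remaining is p / [p + (1 − p)(1 − r)]. At r = 16/54 in both arms, a true 60% v 40% (20 points) becomes 19.4 points, and 80% v 50% (30 points) becomes 26.3. Loss of failures does not always inflate the difference.

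**No true effect.** Assume 30% response in both arms, 40 per arm, and random loss of failures only. Two-sided rejection by Fisher's test was found by simulation (at least 20,000 trials per case).

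| Failures lost, one arm v the other | Expected bias in the difference | Fisher rejection |
|---|---|---|
| none | 0 | about 3% |
| equal | 0 | about 4% |
| 20% v 40% | 0.3/0.72 − 0.3/0.86 = 6.8 points | about 7% |
| 10% v 40% | 0.3/0.72 − 0.3/0.93 = 9.4 points | about 10% |

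The bias favours whichever arm loses more failures. For 20% v 30% the rejection rate stays between 4% and 5%.

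**One data set.** 14/40 v 6/40 gives Fisher p = 0.069. Removing eight failures from the first arm only gives 14/32 v 6/40, p = 0.009. Removing eight from each arm gives 14/32 v 6/32, p = 0.058.

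**Power (exact Fisher).**
- 32 completers per arm, 50% v 15%: 81.5%.
- All 40 per arm, missing counted as non-response, 20% dropout unrelated to response (0.8 × 50% = 40% v 0.8 × 15% = 12%): 77.6%.
- All 40 per arm, dropouts already failures (rates stay 50% v 15%): 89.8%.

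**The case against.** A reader might infer that the plan prescribes a completer analysis, because Section 13.2 applies undiluted rates to 30 men and then adds slots for attrition. The documents do not support that. Inflating enrolment for dropout is routine under any analysis set and fixes none, and the endpoint's reference to subjects in each group can equally mean all randomised men.

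The link to PDE5i is also an inference. Section 7.4(d) is discretionary, does not define non-compliance and does not mention PDE5i. De-enrolment applies to men who complete all visits too, so it does not by itself mean that data are discarded. Men who cannot keep the wash-out are screen failures (Section 6), which removes some likely violators before randomisation.

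On size, a tempting illustration removes eight failures from each arm: 20/32 v 6/32, or 62.5% v 18.75%, a gap of 43.75 points. That is not a neutral case. It takes 8/20 = 40% of PRP failures but only 8/34 = 24% of placebo failures. The 10% type I error needs about 0.7 × 40% = 28% of one arm to leave against 0.7 × 10% = 7% of the other, which is a lot under double blinding. Finally, Section 13.2 does not tie its 20% attrition to the primary visit, and follow-up runs to week 24.

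All of this limits the strength of the claim. It does not remove the gap: a stated rule permits withdrawal after randomisation on a ground plausibly related to outcome, and nothing says that the score is still collected or how the man counts. Wash-out screening acts before the men know whether treatment has worked, and blinding makes unequal loss less likely but cannot exclude it.

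**Conclusion.** The concern holds as a statement of what can happen under the plan, not of what the plan orders. Following Sections 7.4(d) and 8.2.6 as written can lose week-4 outcomes in a response-related way, and Section 13.1 gives no denominator that would protect the comparison.

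The harm is modest if failures leave both arms at the same rate: about 3.6 points of inflation at the planned rates, and no excess of false positives. It becomes material when losses differ clearly by arm. A reader might infer that the bias always favours PRP, but neither its direction nor its size is fixed. The loss rates by arm, the 30% null rate and the placing of all attrition on failures before week 4 are my assumptions; the documents give only the overall figure of about 20%. The point should be settled before unblinding because the remedy is specific and cheap.

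**What to change.** In Section 7.4, state that non-compliance or PDE5i use does not end follow-up, and that the week-4 IIEF is collected from every randomised man who has not withdrawn consent. This concerns data collection only and leaves the PDE5i ban and clinical decisions unchanged.

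In Section 13.1, state that:
- the primary Fisher comparison includes all randomised men in their assigned arm;
- a missing week-4 score counts as non-response, with multiple imputation as the sensitivity analysis;
- scores obtained after PDE5i use are handled by a prespecified rule. Non-response in the primary analysis, with the observed score as sensitivity analysis, is one option. Using the observed score whatever the man took is another. They answer different questions, so the choice must be written down.

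The cost is wording, a little more follow-up and one or two extra analyses. Power need not suffer: at 40 per arm it is 77.6% if the 20% dropout is unrelated to response and 89.8% if dropouts are already failures, against 81.5% for 32 completers per arm.

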| STUDY DESIGN | Randomized, Double Blind, Placebo Controlled, Pilot Trial |
| ROUTE OF ADMINISTRATION | Intracavernosal Injection |
| SUBJECT POPULATION | 80 male subjects between the age of 30-75 with erectile dysfunction of organic origin |
| STUDY OBJECTIVES | 
Primary: To investigate and compare the treatment efficacy of PRP vs placebo treatment in men with mild-moderate ED, as measured by IIEF.
 
Secondary: To study incidence of adverse events and safety of PRP injection treatment in men with mild-moderate ED, as measured by IIEF.
 |
| INVESTIGATION PLAN | 
80 men with Erectile Dysfunction (ED) of organic origin, that meet all of the inclusion and none of the exclusion criteria, will be randomized to receive, intracavernosal injection of either PRP or placebo in a 1:1 double-blinded fashion:
 
Group A (40 subjects): Autologous PRP All subjects in this group will receive 2 sessions of autologous PRP with 30 ± 7 day treatment interval. 5mL of PRP will be injected at each session.
 
Group B (40 subjects): Placebo (Normal Saline) All subjects in this group will receive 2 sessions of normal saline with 30 ± 7 day treatment interval. 5mL of normal saline will be injected at each session.
 
 - Patients will be followed for outcome assessments at 1, 3, and 6 months post final injection. |
| DURATION OF STUDY | 9 months (1 month screening, 2 therapy sessions 1 month apart, 6 months follow-up) |
| DEFINITION OF ENDPOINTS | 
Primary Endpoint (Efficacy)
 
 - The percentage of subjects in each group who attain MCID in IIEF-EF domain from baseline to 4 weeks after final treatment. 
Secondary Endpoints (Efficacy)
 
 - The percentage of subjects in each group who attain MCID in IIEF-EF domain from baseline to 12 & 24 weeks after final treatment. - The difference between groups in change of IIEF-EF score from baseline to 4, 12, & 24 weeks after final treatment. - Differences in Doppler ultrasound parameters (PSV and EDV) from baseline to 24 weeks after final treatment. 
Secondary Endpoints (Safety)
 
 - Incidence of adverse events in all patients during the study period. |

| | |
|--------------------|--|

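### The injected volume is contradictory by a factor of two: Section 8 directs 10 mL per session in both arms, the synopsis directs 5 mL, and Section 9.2 limits PRP to 5 mL

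*Combined protocol and SAP*

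**What the plan says.** Three places in the current protocol bear on the volume given at each of the two sessions.

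- Section 8 (Procedures Involved), for Group A: "10mL of PRP will be injected at each session". For Group B: "10mL of normal saline will be injected at each session".
- Protocol Synopsis, Investigation Plan, for Group A: "5mL of PRP will be injected at each session". For Group B: "5mL of normal saline will be injected at each session".
- Section 9.2 (Administration of IP) sets an upper limit of 5 mL for PRP, split into about 2.5 mL for each corpus cavernosum and infused slowly. It gives no separate figure for saline and says only that saline is injected in a similar way.

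Three other sections touch on the matter without settling it. Section 9.1 gives a separator yield of 3 to 10 mL of PRP and allows platelet-poor plasma (PPP) to be added up to a target volume that it does not name. Section 9.4 specifies 10 cc syringes in both arms. Section 8.2.9 sends the reader to Section 9.2 for administration and states no injected volume itself.

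**The concern.** The injected volume is part of the definition of the intervention in both arms. Staff giving PRP cannot follow Section 8 and Section 9.2 together: 10 mL breaks the limit in Section 9.2, and 5 mL departs from Section 8. Staff giving saline face the same choice between Section 8 and the synopsis. The protocol has no rule saying which section prevails, so a monitor could not say which volume is a deviation, and a reader of the results could not state the planned dose with certainty.

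**Working it through.** The volumes side by side:

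| Place | PRP per session | Saline per session |
|---|---|---|
| Synopsis | 5 mL | 5 mL |
| Section 8 | 10 mL | 10 mL |
| Section 9.2 | at most 5 mL | no figure; as for PRP |

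**Step 1: is Section 9.2 consistent with itself and with the synopsis?** Volume per side × number of sides = 2.5 × 2 = 5 mL. This reproduces the limit in Section 9.2 and matches the synopsis.

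**Step 2: size of the conflict.**
- Per session: 10 / 5 = 2-fold.
- Over two sessions: 2 × 10 = 20 mL against 2 × 5 = 10 mL.
- Per side, if split equally: 10 / 2 = 5 mL against 5 / 2 = 2.5 mL.

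**Step 3: can the two volumes be reconciled?**
- 10 mL equals the two-session total at 5 mL each, but Section 8 states its volume for each session.
- Section 9.1 allows PPP to be added. One might then read 5 mL of PRP made up to 10 mL in total. But Section 8 gives its 10 mL as PRP, the synopsis gives 5 mL for the same sessions, and PPP cannot explain the difference in the saline arm.
- A 10 cc syringe holds either volume, and a yield of 3 to 10 mL with PPP top-up could supply either. These facts do not discriminate.

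No reading makes the three places agree.

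**Step 4: would changing Section 8 to 5 mL be enough?** Not quite. Section 9.2 states a maximum, whereas the synopsis states a flat 5 mL. The yield can be as low as 3 mL, and adding PPP is optional in Section 9.1. An injection of 3 mL would therefore still satisfy Section 9.2 while falling 5 − 3 = 2 mL short of the synopsis. The total volume has to be defined as well.

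**Step 5: what else would change if 10 mL were intended?** Section 9.2 fixes the infusion time. At two minutes per side, 5 mL per side runs at 5 / 2 = 2.5 mL/min, against 2.5 / 2 = 1.25 mL/min as now described. No section prescribes this combination. It shows only that the time could not be left as it is, since Section 9.2 specifies slow infusion to protect the platelets.

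**The case against.** The best defence is that the protocol as a whole points to 5 mL. The synopsis says so for both arms, Section 9.2 is the detailed procedure, and Section 8.2.9 directs staff there. The trial has no additional sites, so a single team is likely to settle on one practice. Both 5 mL and 10 mL are stated symmetrically for the two arms, so the comparison stays matched either way. Most of this stands and limits the practical risk. Section 8.2.9 is not a further source for 5 mL, however, because it only refers to Section 9.2. Section 8 is itself operative text and cannot be set aside without a rule of precedence.

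A reader might also infer that the 10 mL is simply left over from an older text. The opening sentence of Section 8 counts "72 men with Erectile Dysfunction (ED) of organic origin", whereas Section 6 gives "80 males with ED of organic origin". The figure 72 equals 2 × (30 + 6), the per-group numbers in Section 13.2, so that sentence may not have been updated when the total became 80. The documents do not carry the inference over to the volume. The 10 mL figures stand in the very items that carry the current group size, "Group A (40 subjects): Autologous PRP injection" and "Group B (40 subjects): Placebo (Normal Saline"), and 40 + 40 = 80. If those items were revised, the volumes in them may have been looked at too. The 10 cc syringes and the upper end of the yield range are also compatible with 10 mL.

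**Conclusion.** The contradiction is real, lies in current operative text and should be fixed. The planned dose is ambiguous by a factor of two: 10 or 5 mL per session, 20 or 10 mL over two sessions. For PRP, Section 8 directs twice the maximum in Section 9.2. For saline, the explicit conflict is Section 8 against the synopsis, because the limit in Section 9.2 names PRP only. The weight of the text favours 5 mL, but which figure is outdated is not shown.

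The conclusion rests only on the stated volumes and on the absence of a rule of precedence. The per-side figures for 10 mL assume an equal split.

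A reader might go further and infer that subjects received mixed volumes, or that the discrepancy biases the comparison, breaks the blind, causes harm or weakens the power. The documents support none of these. They contain no record of volumes given, each conflicting volume is the same in both arms, the colored and covered syringes in Section 9.4 can hold either, and the sample size calculation in Section 13.2 does not use the volume.

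**What to change.** The sponsor should confirm the intended volume and then state one figure in the synopsis, Section 8 and Section 9.2.

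- **If 5 mL**, as the synopsis and Section 9.2 indicate: change both 10 mL statements in Section 8 to 5 mL. State in Sections 9.1 and 9.2 that 5 mL is the total injected volume in both arms, meaning PRP plus any PPP in the active arm and saline in the control arm. The content of PRP within the 5 mL would still vary with yield: if PRP is used first, min(yield, 5) runs from 3 to 5 mL. The correction settles the volume, not the platelet dose.
- **If 10 mL**: amend both volumes in the synopsis, and the maximum, per-side volume and infusion time in Section 9.2.

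The cost is a few words and numbers. Correcting to 5 mL needs no extra patients, visits, procedures or data.
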